1.1 Funding

NSW Health is funding the development, implementation, and monitoring of the trial through a grant awarded to a consortium of universities and academics led by Chief Investigator, [name] from the University of Newcastle, titled *NSW Government-Sponsored Clinical Trial: Management of Urinary Tract Infections by Community Pharmacists to include oral contraception and management of minor skin conditions*. This protocol is to undertake the Intervention study for the dermatology phase.

1.4 Glossary of abbreviations and terms

ACT	Australian Capital Territory
APDC	Admitted Patient Data Collection
ARF	Acute rheumatic fever
CARPA	Central Australian Rural Practitioners Association
CFIR	Consolidated Framework for Implementation Research
ED	Emergency Department
EDDC	Emergency Department Data Collection
EPA	Extended Practice Authority

GDS	George Data Systems
GP	General Practitioner
HREC	Human Research Ethics Committee
ID	Identification
MBS	Medicare Benefits Schedule
MMM	Modified Monash Model
NPT	Normalisation process theory
NSW	New South Wales
PSA	Pharmaceutical Society of Australia
PBS	Pharmaceutical Benefits Scheme
RHD	Rheumatic heart disease
SEIFA	Socioeconomic indexes for area
TGI	The George Institute for Global Health
UoN	University of Newcastle

2. Protocol Synopsis

The overall aim of this study is to evaluate the clinical and economic impact and implementation of a service model (intervention) delivered by community pharmacists in New South Wales (NSW) and 15 pharmacies in the Australian Capital Territory (ACT), managing four skin conditions for individuals presenting with a suspected diagnosis – Impetigo, Atopic Dermatitis, Mild Plaque Psoriasis and Herpes Zoster.

The specific objectives of this study are to:

1. Assess implementation uptake of the intervention including the reach, fidelity and adoption of the intervention in community pharmacies, participant characteristics, and variation in uptake by geographic region.
2. Assess the clinical outcomes and patient experience for patients managed by community pharmacists.
3. Assess the safety of the intervention and identify any risks that need to be addressed for future implementation.
4. Qualitatively assess the acceptability and feasibility of the intervention to pharmacists, other care providers and participants using the service.
5. Identify contextual enablers and constraints to access, adoption, fidelity, delivery, impact, sustainability, and generalisability of the intervention.
6. Conduct a health economic evaluation to determine the economic benefits.

The study will use a cohort study design to assess the clinical and economic impact and implementation of the intervention in NSW and ACT. Pharmacies will be onboarded from June 2024 to September 2024. This is due to administrative processes associated with MedAdvisor program installation, and the numbers of pharmacies that can be onboarded will be batched over this time. The study will be completed when 22,857 consults are reached or on 28 February 2025, whichever occurs first.

The intervention is multicomponent including Pharmacist training and support, and a Pharmacist-patient consultation, using an IT program, applying clinical guidelines. Pharmacies and pharmacists must meet the criteria of an 'approved pharmacy' and an 'approved pharmacist' outlined in the NSW Health Authority (Appendix 1), or a licence in ACT, to participate.

The 'approved pharmacist' will follow clinical practice guidelines originally developed by Queensland Health (Appendix 2). These guidelines have been through a co-design process (part of a separate low-risk ethics submission approved by HREC – University of Newcastle - H-2023-0448) and their content validated by dermatologists, GPs and NSW Health. These guidelines include a process for the pharmacist to make clinical decisions, and refer to other health professionals, particularly general practitioners.

The 'approved pharmacist' must complete the:

- Australasian College of Pharmacy modules on dermatology conditions; or

- Pharmaceutical Society of Australia module on dermatology conditions; and
- Modules developed by the University of Newcastle.

Pharmacists and pharmacies will be provided follow up support as part of a translational/ implementation strategy. Practice change facilitators will visit/contact these pharmacies during the study to provide ongoing support, answer any queries, ensure quality data is being collected, and collect implementation data. Pharmacies will be divided into low, medium and high contact, and this will depend on the number and nature of consultations delivered throughout the trial period.

The primary outcome will be symptom resolution/relief (completely resolved, improvement, no improvement or worsening) (based on self-report at 7-day or a 14 day follow up (depending on the skin condition)). This will be a composite measure based on patient self-reported data. As symptom resolution/relief time can be different for each of the four conditions, follow-up periods according to the clinical practice guidelines will be:

- 7 days for Impetigo, Psoriasis and Herpes Zoster (Shingles)
- 14 days for Atopic Dermatitis.

There will be several secondary outcomes which will be derived from the IT consultation database, patient follow-up, and an implementation database. In addition, qualitative methodology in the form of semi-structured interviews will be conducted with pharmacists and other stakeholders to better understand barriers and facilitators to implementation of the service (Appendix 3-4).

3. Introduction

3.1 Background to community pharmacy prescribing

On an international and national basis, the scope of practice for community pharmacists is evolving rapidly. The NSW and ACT Governments have recognised the expanded role community pharmacists could play. The broad approach is to increase the community's access to primary care through:

1. Authorising pharmacists to administer a wider range of public health and travel vaccinations from 14 November 2022, including Japanese Encephalitis, Hepatitis A and Hepatitis B, Poliomyelitis, Typhoid and Zoster.
2. Funding a 12-month trial to evaluate pharmacists managing uncomplimented urinary tract infections in a specified cohort of females.
3. Funding a 12-month trial to evaluate pharmacists extending the supply of certain low risk oral contraceptive pills (OCPs).
4. Supporting a state-wide trial where appropriately trained pharmacists can prescribe medications for certain conditions, such as skin ailments [1].

This study protocol refers to the fourth goal above.

International context – The evolution of a community pharmacy in Australia has mirrored international trends. In New Zealand (NZ) there has been an emphasis on integration, spanning primary care and secondary care [2]. This has also occurred in the United Kingdom (UK), where pharmacists are seen as part of the integrated solution to patient and healthcare demands [2]. In the United States, pharmacists are being recognised as part of integrated teams, with opportunities provided by a proliferation of new models such as medical homes, and community-based care teams [3]. Canada, the UK and NZ are more advanced in terms of the enhancing pharmacist roles and scope of practice in areas such as minor ailments or common clinical conditions, pharmacist prescribing, personalised medicines support and screening, and chronic disease prevention [4].

Australian context – An environmental scan provides evidence that at the Australian State and Federal level there has been a significant number of changes. A significant announcement has been the commencement of service delivery in the Queensland pilot trial in May 2024 and that it will be offered statewide and not restricted only to North Queensland. In addition, several other states including Victoria, South Australia and

Tasmania, have made similar announcements. These changes suggest that there is a high probability that pharmacist prescribing in Australia may become usual practice.

In NSW, a urinary tract infection (PATH-UTI) and oral contraceptive pill (PATH-OCP) have commenced. Both trials have been registered with ANZCTR (ACTRN12623000882628 and ACTRN12623001124628, respectively) and previously approved by The University of Newcastle Human Research Ethics Committee (H-2023-0119 on the 27/06/2023 and H-2023-0234 on the 25/08/2023, respectively). The proposal from the NSW Ministry of Health is to implement a third trial on the dermatological conditions (PATH-DERM). These trials have been designed to explore various aspects of pharmacy prescribing and have a secondary objective to lay foundational blocks to prepare the NSW pharmacy workforce. Importantly, it would enable the NSW Government to have community pharmacy and community pharmacists as a resource for the NSW population for the delivery of high-quality primary health care and public health initiatives.

3.2 Aim and objectives

3.2.1 Aim

The overall aim of this study is to evaluate the clinical and economic impact and implementation of a service model (intervention) delivered by community pharmacists in New South Wales (NSW) and 15 pharmacies in the Australian Capital Territory (ACT), managing four skin conditions for individuals presenting with a suspected diagnosis – Impetigo, Atopic Dermatitis, Mild Plaque Psoriasis and Herpes Zoster.

Pharmacies will be onboarded from June 2024 to September 2024. This is due to administrative processes associated with MedAdvisor program installation, and the numbers of pharmacies that can be onboarded will be batched over this time. The study will be completed when 22,857 consults are reached or on 28 February 2025, whichever occurs first.

3.2.2 Objectives

The specific objectives of this study are to:

1. Assess implementation uptake of the intervention including the reach, fidelity and adoption of the intervention in community pharmacies, participant characteristics, and variation in uptake by geographic region.
2. Assess the clinical outcomes and patient experience for patients managed by community pharmacists.
3. Assess the safety of the intervention and identify any risks that need to be addressed for future implementation.
4. Qualitatively assess the acceptability and feasibility of the intervention to pharmacists, other care providers and participants using the service.
5. Identify contextual enablers and constraints to access, adoption, fidelity delivery, impact, sustainability, and generalisability of the intervention.
6. Conduct a health economic evaluation to determine the economic benefits.

4. Methods

4.1 Study hypothesis

The study hypothesis is that the community pharmacy delivered services for four skin conditions will: (1) achieve high rates of implementation and adherence to treatment protocols; (2) result in self-reported symptom resolution/relief rates at various time interval depending on the condition; and (3) not be associated with safety risks.

4.2 Study design

[figure not shown]
The study hypothesis will be tested using a cohort study design, applying mixed methods (quantitative and qualitative research) to assess clinical and economic indicators, implementation, and patient experience.

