4.9 Outcomes

Primary outcome

The primary outcome will be symptom resolution/relief (completely resolved, improvement, no improvement or worsening) (based on self-report at various time frames at follow up depending on the condition). This will be a composite measure based on patient self-reported data. As symptom resolution/relief time can be different for each of the four conditions, follow-up periods according to the clinical practice guidelines will be:

- 7 days for Impetigo, Psoriasis and Herpes Zoster (Shingles)
- 14 days for Atopic Dermatitis

Secondary outcomes

Secondary outcomes will be:

- Types of medication supplied for each condition by pharmacists. This is a participant specific outcome.
- Adherence rates to treatment protocol. This is a pharmacy-specific outcome.
- Numbers of patients supplied medications by pharmacists. This is a participant specific outcome.
- Numbers of patients provided self-care advice. This is a participant specific outcome.
- Numbers of patients referred to another health professional. This is a participant specific outcome.
- Reasons for patient referral to another health professional. This is a participant specific outcome.
- Estimated duration of consultation. This is a pharmacy specific outcome.
- Patient follow-up rate. This is a participant specific outcome.
- Patient adverse events. This is a participant specific outcome.
- Patient experience. This is a participant specific outcome.
- **Safety outcomes:** Patient-reported adverse events defined as any unfavourable and unintended sign, symptom or disease associated with the use of a medicine, which does not necessarily have to be caused by that medicine (Appendix 25).
- **Implementation outcomes**
 - Patient and provider program participation rates
 - Patient demographics (gender, DOB, education, employment status)
 - Numbers of patients per pharmacy assessed as eligible for pharmacy medication supply.
 - Numbers of patients supplied medication by pharmacists.
 - Estimated duration of consultation
 - Estimated time to complete all service requirements.
 - Adherence rates to treatment protocol
 - Prescriptions for first-line medications for the four skin conditions /Total medication prescriptions for the four skin conditions
 - Classification of appropriateness of medications for the four conditions as aligned with clinical practice guidelines.

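### The protocol promises to test its hypothesis, but as worded any result satisfies part 2, and part 3 cannot be identified in a cohort with no comparator or reference rate

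*Protocol*

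**What the plan says.** Section 4.1 states one hypothesis in three parts. Part 1 concerns delivery and expects the service to "achieve high rates of implementation and adherence to treatment protocols". Part 2 turns to the primary outcome and expects the service to "result in self-reported symptom resolution/relief rates at various time interval depending on the condition". Part 3 deals with harm and expects the service to "not be associated with safety risks". On how these are to be examined, section 4.2 says "The study hypothesis will be tested using a cohort study design".

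Section 4.4 has the pharmacist offer participation to every presenting patient who meets the inclusion criteria, and the consultation is the only pathway studied. Section 4.9 defines the primary outcome as a self-report in four categories, collected at 7 days for three conditions and at "14 days for Atopic Dermatitis". The safety outcome in the same section counts patient-reported events whether or not the medicine caused them. Section 4.10.1 plans descriptive statistics, regression adjusted for age, and subgroup analyses within the cohort.

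None of these sections names a control group, a historical control, a target rate or a margin. The figure in section 4.2 is not shown in the copy at hand, but no text refers to a comparator. Objectives 2 and 3 in section 3.2.2 are more modest: they speak of assessing outcomes and safety and of identifying risks.

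**The concern.** A hypothesis can be tested only if some result would count against it and the design can produce that result. Part 2 fails the first condition. Part 3 fails the second, because a statement about association compares the event rate under the service with a rate that the study neither measures nor cites.

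At stake is what may be concluded at the end. Under the present wording, a good improvement rate at 7 or 14 days could be reported as support for part 2, although natural recovery cannot be separated from the effect of the service. A low count of reported events could be reported as support for part 3, although background events cannot be separated from those due to the service. The count may also be incomplete. Section 4.6.2 treats patients who do not answer after three reminders as lost to follow-up, and section 4.4.1 removes the data of patients who withdraw.

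**Working it through.** The protocol states no significance level, power, reference rate or margin, so there is no figure of its own to reproduce. The check takes the parts in turn.

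**Inputs from the protocol.** The study ends at 22,857 consults or on 28 February 2025, whichever comes first.

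**Assumptions.** The cap is reached, each consult is one patient, and survey response lies between 20% and 100% (no rate is stated). The event and background rates below are illustrative.

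**Part 1.** It has a direction (high) but no value. Low adherence would plainly count against it, but where low ends is not stated.

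**Part 2.** Let X be the number of n respondents who report resolution or relief, with true rate p. With no threshold, the success rule is X ≥ 0, and P(X ≥ 0) = 1 for every p, including p = 0. A kinder reading is that at least one patient reports relief. Then P(X ≥ 1) = 1 − (1 − p)^n. With p = 0.1% and n = 11,428 (50% response), this is 1 − 0.999^11,428 = 1 − 0.00001 = 0.99999. Either way the statement does not discriminate.

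**Part 3, read as a statement of association.** Excess = observed rate − background rate. Take 571 events in 11,428 respondents. The rate is 571 / 11,428 = 5.0%, with an exact 95% interval of 4.6% to 5.4%. The rate itself is well estimated, but the excess is not:

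| Assumed background rate | Excess |
|---|---|
| 2% | 5.0 − 2 = +3.0 points |
| 5% | 5.0 − 5 = 0.0 points |
| 8% | 5.0 − 8 = −3.0 points |

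Even the sign depends on a quantity that the study does not observe. A larger n narrows the interval but does not supply the background rate.

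**Part 3, read literally as no events.** P(no events) = (1 − p)^n. At p = 0.1% this is about 1 × 10⁻¹⁰ for n = 22,857, about 1 × 10⁻⁵ for n = 11,428, and about 1% for n = 4,571 (20% response). On this reading part 3 would almost certainly be contradicted, so it is not safe from refutation.

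**What the design can do.** The half-width of a 95% interval for a 50% resolution rate is 1.96 × √(0.25 / n): 0.65 points at n = 22,857, 0.92 at n = 11,428 and 1.45 at n = 4,571. If no event of a given type is reported, the upper limit of the exact two-sided 95% interval is 1 − 0.025^(1/n). That is 5.4, 3.2 and 2.3 per 10,000 at 30%, 50% and 70% response (n = 6,857, 11,428 and 15,999). These figures describe precision only and do not measure the fault in parts 2 and 3. They ignore clustering by pharmacy and the split into four conditions, so real intervals will be wider.

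**The case against.** The strongest reply is that the protocol is descriptive in everything but one word. The objectives say assess and identify, section 4.10.1 contains no formal test, section 4.10.3 admits that the cohort design limits the cost analysis, and section 4.11 gives safety review to a monitoring board. Thresholds and success criteria are often left to a statistical analysis plan, which is not shown here. An uncontrolled cohort can also support an absolute safety statement, such as an upper confidence limit for an event rate below a pre-set value.

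Much of this stands. The missing number in part 1 would be a small matter on its own, and an absolute limit would rescue a reworded part 3. But an analysis plan cannot supply a comparator that the design lacks, nor make part 2 refutable while its wording remains. The monitoring board has no stated numerical criterion and does not test part 3. The descriptive objectives show that sections 4.1 and 4.2 promise more than the rest of the protocol.

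Three stronger readings are tempting, and the document does not support them:

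- **The study will confirm its whole hypothesis whatever happens.** This is true only of part 2. Poor adherence would contradict part 1, and a cluster of serious events would count against part 3.
- **The protocol claims effectiveness or safety against usual care for symptoms or harms.** It nowhere says so. The risk lies in how parts 2 and 3 could be reported.
- **The fault is too few patients for rare events.** Small rare-event rates would be hard to compare even with a control group of this size. Whether serious events are captured only by the survey cannot be known either, because the adverse event policy (Appendix 25) is not at hand.

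**Conclusion.** The point holds for the wording of parts 2 and 3 and for the promise in section 4.2 to test them. Part 2 is satisfied by every possible data set. Part 3 is not identifiable as worded: in the illustration the excess runs from +3 to −3 points as the assumed background rate moves from 2% to 8%. Part 1 has the milder weakness of a direction without a value.

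The conclusion on parts 2 and 3 rests on the wording and on the absence of any comparator or reference rate in the text. It does not depend on the assumed response or event rates, which serve only as illustration. Recruitment, data collection and outcomes are unaffected. What changes is what the study may claim, so the wording should be corrected before results are reported.

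**What to change.** In sections 4.1 and 4.2, replace testing with an estimation aim that matches objectives 2 and 3:

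1. Estimate adherence to the treatment protocols, with 95% intervals.
2. Estimate symptom resolution/relief separately for each condition, with 95% intervals.
3. Estimate adverse event rates, with upper 95% limits.

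Delete "not be associated with safety risks". Add a sentence saying that the uncontrolled cohort supports no claim of effectiveness or safety relative to usual care or natural recovery. If limits for zero observed events are quoted, label them as precision under an assumed response rate with the consult cap reached.

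This needs no new data, comparator or benchmark. The cost is an amendment to two short sections and a less favourable headline claim.

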4.3 Pharmacy and pharmacist recruitment

Consent will be sought at two levels: the pharmacy level from pharmacy owners, and from the individual pharmacists in those pharmacies to participate in the study.

Please refer to Figure 1 which outlines the process for recruitment and contact with pharmacies and pharmacists. Both NSW and ACT will follow the same process with ACT commencing from Box 2, Figure 1.

Figure 1: Pharmacies and Pharmacists recruitment process for the Dermatology trial

NSW and ACT pharmacies

The contractual arrangements with the NSW Ministry of Health oblige us to offer participation to all NSW pharmacies who had consented to either of the previous trials (PATH-UTI and PATH-OCP) (ACTRN12623000882628 and ACTRN12623001124628, respectively).

Firstly, the list of NSW pharmacies currently participating in the PATH-UTI and/or PATH-OCP trials will be prepared (Box 1, Figure 1). The 15 participating pharmacies in the PATH-UTI and/or PATH-OCP from the ACT will also be added to this list.

An initial email will be sent to pharmacy owners to inform them about the dermatology trial and offer voluntary participation in the trial (Appendix 5, Email 1). This email will provide details of the trial including the NSW Health Authority or ACT Health licence, the Clinical Guidelines and specifying that 3 days later a DocuSign will be sent including Participant Information Statement and Consent form. The voluntary nature of their participation will be reiterated at this point (Box 2, Figure 1). If communication is received at this time that a pharmacy does not wish to participate, no further contact will be made (Box 2a, Figure 1).

A DocuSign will be sent to all pharmacy owners three days after Email 1, providing the Pharmacy Participant Information Statement and Consent form (Appendix 5, Email 2) (Box 3, Figure 1) (Appendices 6-9). The pharmacy owner may include additional pharmacists who have expressed their interest in participating during the consent process by completing the table provided in the pharmacy consent form.

For those pharmacy owners that have not yet provided consent, a reminder after 10 days will be sent (Appendix 5, Email 3), with a second reminder a week later (Appendix 5, Email 4). If the pharmacy owner does not respond after the second reminder it will be presumed that their pharmacy does not wish to participate, and the research team will not contact them any further. Alternatively, if they decline at any time to participate in the trial. The research team will not contact them any further (Box 3a, Figure 1).

Following consent by the pharmacy (Box 4, Figure 1), pharmacists in consented pharmacies will be contacted about the dermatology trial and offer voluntary participation in the trial (Appendix 5, Email 5). This email will provide details of the trial including the NSW Health Authority or ACT Health licence, the Clinical Guidelines and specifying that a DocuSign will be sent including Participant Information Statement and Consent form, following training completion. Details of the required training and how to access will be provided. The voluntary nature of their participation will be reiterated at this point (Appendix 5, Email 5).

Training completion will be verified by a member of the research team in our databases (Box 5, Figure 1), where a DocuSign providing the Pharmacist Participant Information Statement and Consent form will be sent (Appendix 5, Email 7) (Box 6, Figure 1) (Appendices 10-13). For pharmacists who have not completed the training, a single reminder will be sent via email after 30 days (Appendix 5, Email 6). No further contact will be made thereafter.

For those pharmacists that have not yet provided consent despite completion of training, a reminder after 10 days will be sent (Appendix 5, Email 8), with a second reminder a week later (Appendix 5, Email 9) (Box 6a, Figure 1). If the pharmacist does not respond after the second reminder it will be presumed that they do not want to participate, and the research team will not contact them any further. Alternatively, if they decline at any time to participate in the trial, the research team will not contact them any further.

A research team member will verify in our database that a consented pharmacy has at least 1 consented pharmacist (as per the legislative requirements of the NSW Health Authority and ACT Licence) (Box 7, Figure 1). The research team will notify MedAdvisor to activate pharmacy prescribing software in the consented pharmacy and will notify NSW Health for inclusion of the pharmacy to be listed on 'Find A Pharmacy' (Box 8, Figure 1). Consented pharmacies and pharmacists will be contacted by email regarding service commencement, listing on 'Find a Pharmacy' and emailed the NSW Health dermatology trial communications toolkit (Appendix 5, Email 10) (Box 9, Figure 1).

Any request from pharmacies not participating in the PATH-UTI and/or PATH-OC trials to participate in the dermatology trial will be reviewed on a case-by-case basis by the leadership team, and as per contract requirements, NSW Health advice will be sought (Box 1a, Figure 1).

